2 PROTOCOL SYNOPSIS

Product:	ZADAXIN® (thymalfasin/Ta1) lyophilisate for solution for injection
Title of Study:	A Pilot Trial of Thymalfasin (Ta1) to Prevent COVID-19 Infection in Elderly Renal Dialysis Patients
Phase of Development:	Pilot Study
Background and Rationale:	
Ta1 is a naturally occurring peptide with immunomodulatory activities. ZADAXIN® Ta1 is a synthetic version currently approved for use in 37 countries; in particular it is approved in China hepatitis B and to enhance vaccine response. Ta1 has also been studied in multiple clinical trials in the United States. Ta1 has been used clinically in pilot studies for treatment of SARS and other lung infections including acute respiratory disease (ARD) and chronic obstructive pulmonary disorder (COPD), as well as infections after bone marrow transplant. The beneficial clinical effects of Ta1 result from activation of toll-like receptor (TLR) 9 in dendritic and other immune system cells, resulting in augmentation of T helper (Th1) function, natural killer (NK) cell activity, and increased antibody responses to T-cell dependent antigens. Importantly, Ta1 also leads to an increase in IL-10 producing regulatory T cells, which create feedback inhibition of cytokine production, hence dampening immune response and preventing a pro-inflammatory cytokine storm.
 
Based on post-marketing treatment experience of more than 600,000 patients, Ta1 has been well tolerated. Ta1 has been administered to elderly subjects (up to 101 years old), children (as young as 13 months), and immunocompromised patients. The most common adverse events in previous clinical trials include injection-site pain (such as burning and itching) which was mild and lasted for less than 30 minutes, as well as fever, nausea, and flu-like symptoms which were mild to moderate in severity. Thus, while Ta1 is one of only a few immunomodulatory agents that have been approved for human use, it does not appear to induce most of the side effects and toxicities commonly associated with other biological response modifiers (BRMs) in this class, such as interferon and interleukin-2.
 
The actual dose, frequency, and length of treatment with Ta1 have differed depending upon the indication, ranging from 1.6 mg twice a week for up to 12 months; 1.6 mg twice a day

Clinical Study Protocol: Ta1 to Prevent COVID-19 Infection in Elderly Renal Dialysis Patients

	
for several weeks; 6.4 mg daily, 4 days a week, for 2 weeks out of every month up to 6 months in duration; and 16 mg twice a week for four weeks, with few adverse events observed. The proposal to evaluate Ta1 at a dose of 1.6 mg is based on previous studies which have shown an increase in dose above 1.6 mg to show little, if any, improvement in response.
 
Patients with end-stage renal disease (ESRD) on hemodialysis, in addition to their intrinsic kidney disease and frequent burden of comorbidities, also have increased risk of exposure to communicable diseases as they are treated several times each week at hemodialysis centers with several other patients and clinic staff in attendance. The majority of patients are over 60 years of age and many are receiving immunosuppressive medications. Accordingly, ESRD patients are particularly susceptible to COVID-19 infection. Ta1 has been shown to be safely administered to hemodialysis patients on a similar schedule to that proposed below, and was efficacious in enhancing influenza vaccine responses [1].

Objectives:	
Primary Objective
 
To demonstrate that Ta1 administered twice weekly for eight weeks to renal dialysis patients 60 years and older will reduce the incidence of COVID-19 infection compared with a similar population of patients who do not receive Ta1.
 
Secondary Objectives
 
1. To demonstrate that renal dialysis patients treated with Ta1 who become infected with COVID-19 will have a milder course of infection in terms of hospitalization rate, requirement (length) for ICU stay, requirement for mechanical ventilation, and survival than renal dialysis patients not treated with Ta1.2. To demonstrate a decrease in hospitalization rates in renal dialysis patients treated with Ta1 who are not infected with COVID-19 compared to those not treated with Ta1.
Study Design:	
It is our hypothesis that a course of Ta1 administered to individuals at high risk for COVID-19 infection will reduce the rate of infection (primary objective) and severity of infection (secondary objective) with COVID-19, compared to untreated individuals in the same hemodialysis units with

Clinical Study Protocol: Ta1 to Prevent COVID-19 Infection in Elderly Renal Dialysis Patients

	
comparable risk. The secondary objectives also include an evaluation of the need for hospitalization in those patients who do not become infected with COVID-19.
 
Ideally, a randomized clinical trial with placebo control would be a preferred approach to address this hypothesis. However, the urgency of the current situation necessitates a simpler research design and implementation. Accordingly, we consider this a pilot study from which meaningful clinical data may rapidly be apparent.
 
After screening, renal dialysis patients 60 years and older who meet the inclusion criteria will receive Ta1 (1.6 mg) administered subcutaneously (SC) twice weekly for eight weeks. Individuals in the control arm will be followed on the identical protocol but will not receive twice weekly Ta1. After the treatment period, all subjects will be followed for efficacy outcomes for an additional 4 months.

Sample Size:	A total of up to 240 patients will be enrolled
Countries:	U.S.
Study Period:	Once FDA and IRB approval are obtained, the research team will promptly initiate the process of subject recruitment. Recruitment of all subjects will be completed in four months and the observation phase in one year.
Diagnosis and Main Criteria for Inclusion:	
 1. Age 60 or greater 2. Signed informed consent 3. End-stage renal disease (ESRD) who receive hemodialysis 2 or more times each week and are expected to continue on dialysis indefinitely.
Main Exclusion Criteria:	
 1. Patients on short-term hemodialysis, such as those with transient renal dysfunction associated with acute illness who are projected to have return in renal function 2. Patients for whom renal transplantation is anticipated within the next six months 3. Patients with an anticipated survival of less than 3 months 4. Patients with symptoms that might be attributable to COVID-19 infection (see Appendix 1 for symptom questionnaire) 5. Patients who test positive for SARS-CoV2

Clinical Study Protocol: Ta1 to Prevent COVID-19 Infection in Elderly Renal Dialysis Patients

	
 6. Patients with active infectious disease requiring antibiotics 7. Patients with hospitalization within the previous 3 months for acute myocardial infarction or congestive heart failure 8. Patients with advanced malignancy receiving cytotoxic chemotherapy 9. Patients with a Karnofsky Performance Scale score of less than 60 10. Patients with prior history of solid organ (kidney, liver, heart, lung, pancreas) or bone marrow transplant 11. Patients with active autoimmune disease on immunosuppressive medication 12. Patients receiving Plaquenil 13. Participation in an investigational drug or device trial in previous 30 days 14. History of allergy or intolerance to Ta1 15. Any other medical or psychiatric condition that, in the opinion of the Investigator, would compromise patient safety or interfere with the objectives of the protocol or completion of the protocol treatment.
Drug Formulation:	Ta1 is contained, stored, and dispensed from individual tamper-proof glass vials with 1.6 mg Ta1 as a lyophilized cake containing 5% mannitol, buffered with phosphate to pH 6.4-7.3. Vials are reconstituted with 1 mL of supplied diluent (sterile Water for Injection), prior to subcutaneous administration.
Dose and Mode of Administration:	Active arm: 1.6 mg Ta1 in 1 mL SC injection twice weekly after dialysis
Duration of Treatment:	8 weeks
Reference Therapy, Dose and Mode of Administration:	Control arm: standard care
Duration of Treatment:	8 weeks
Randomization:	
Patients will be randomized 1:1
 
Randomization will be stratified by site

Efficacy Endpoints:	Primary Efficacy Endpoint

	
The primary efficacy endpoint is reduction in documented infection with COVID-19.
 
Secondary Efficacy Endpoints
 
The secondary efficacy endpoints are:
 
1. Need for hospitalization2. Hospital length of stay3. ICU admission4. ICU length of stay5. Mechanical ventilation6. Duration of mechanical ventilation7. Recovery time from COVID-198. Change in any existing comorbidities (e.g., worsening congestive heart failure) or occurrence of newly diagnosed disease9. Incidence of non-COVID-19 infections (other respiratory, urinary tract, cellulitis, etc.)10. Change in T lymphocyte subsets (CD4, CD8)11. Mortality
Safety Endpoints:	Adverse events, vital signs, and laboratory parameters

4 ABBREVIATIONS

Abbreviation	Full Term
ADL	activities of daily living
AE	adverse event
ARDS	acute respiratory disease
CBC	complete blood count
CFR	Code of Federal Regulations
CMV	cytomegalovirus
COPD	chronic obstructive pulmonary disorder
CRF	case report form
CRP	C-reactive protein
CTM	clinical trial material (i.e., ZADAXIN or placebo)
ESRD	end-stage renal disease
FDA	Food and Drug Administration
GCP	good clinical practice
HIPAA	Health Insurance Portability and Accountability Act
HIV	human immunodeficiency virus
ICF	informed consent form
ICH	International Conference on Harmonisation
ICU	intensive care unit
IL	interleukin
IND	investigational new drug
IRB	Institutional Review Board
LDH	lactate dehydrogenase
mL	milliliter
mg	milligram
2019-nCoV	2019 novel coronavirus
NK	natural killer
NOEL	no observable effect level
SAE	serious adverse event
SARS	severe acute respiratory syndrome
SC	subcutaneous(ly)
Ta1	ZADAXIN thymalfasin, thymosin alpha 1
Th1	Th1-type T cell
TLR	Toll-like receptor
WHO	World Health Organization

5 INTRODUCTION AND STUDY RATIONALE

5.1 Introduction

In December of 2019 a cluster of unexplained pneumonia cases were reported in Wuhan, China. Shortly thereafter, the causative agent of this mysterious pneumonia was identified as a novel coronavirus [2]. On January 12, 2020 the World Health Organization (WHO) temporarily named this new virus the 2019 novel coronavirus (2019-nCoV) and later named it severe acute respiratory syndrome coronavirus 2 (SARS-CoV-2). In February 2020 the term COVID-19 was introduced as the name of the disease caused by SARS-CoV-2. The COVID-19 epidemic has now reached pandemic proportion and spread beyond China prominently throughout the world including Asia, Europe, United States and over 150 sovereign nations [3-5]. COVID-19 causes a respiratory illness characterized initially by sore throat, fever, cough and malaise but progressing in some patients to lower respiratory infection, respiratory failure and mortality [6]. COVID-19 is highly contagious and it has been projected that as many as 40% of the entire United States population may become infected [7, 8]. One thing that has become increasingly clear is that older individuals, and particularly those with comorbidities and/or immunosuppression are at particularly high risk for adverse outcomes including requiring hospitalization, intensive care management, ventilatory support and mortality [9].

With the current and rapidly expanding burden of infection in the United States there has been great emphasis on disease treatment as well as vaccine development. Indeed, already there are clinical trials of antivirals and/or antimalarials that are currently enrolling patients. Vaccines are also on the fast track for development but it has been projected that their availability will be at least 12-18 months from now.

As we await the availability of an effective vaccine, we propose the investigation of an immune enhancing synthetic peptide with established safety and efficacy in a variety of clinical situations in the context of viral disease. This study should demonstrate feasibility and possibly provide evidence of efficacy. Further, our findings may be particularly valuable once a COVID-19 vaccine is available. At that time there may be efforts to enhance vaccine efficacy among at risk populations, such as in patients of advanced age or with comorbidities. Thymalfsin (thymosin alpha 1 or Ta1), the subject for this research protocol, is also known to provide increased response to vaccines. In previously published Phase 2 clinical trials carried out in the United States in over 400 geriatric (66 to 99 years) and kidney dialysis patients, Ta1 was reported to safely and significantly increase antibody responses to the influenza vaccine and reduce symptoms of influenza following infection [1, 10, 11].

5.2 Background and Rationale

Ta1 is a naturally occurring peptide that has been evaluated for its immunomodulatory activities and related therapeutic potential in several conditions and diseases, including infectious disease and cancer. ZADAXIN® brand Ta1 is a synthetic version currently approved for use in 37 countries; in particular it is approved in China hepatitis B and to enhance vaccine response. Notably, Ta1 has been used clinically in pilot studies for treatment of severe acute respiratory syndrome (SARS) [12] and other lung infections including acute respiratory distress syndrome

Clinical Study Protocol: Ta1 to Prevent COVID-19 Infection in Elderly Renal Dialysis Patients

(ARDS) [13] and chronic obstructive pulmonary disorder (COPD) [14], as well as infections after bone marrow transplant [15]. Larger clinical trials have shown significant efficacy for treatment of severe sepsis [16, 17] and hepatitis B [18], along with certain cancers such as melanoma, hepatocellular, and lung cancer [19]. Ta1 has also demonstrated improvement in response to vaccines in the elderly and in patients immunocompromised by renal disease. The beneficial clinical effects of Ta1 result from activation of toll-like receptor (TLR) 9 in dendritic and other immune system cells, resulting in augmentation of T helper (Th1) function, natural killer (NK) cell activity, and increased antibody responses to T-cell dependent antigens. Importantly, Ta1 also leads to an increase in IL-10 producing regulatory T cells, which create feedback inhibition of cytokine production, hence dampening immune response and preventing a pro-inflammatory cytokine storm.

Based on post-marketing treatment experience of more than 600,000 patients, Ta1 has been well tolerated. Ta1 has been administered to elderly subjects (up to 101 years old), children (as young as 13 months), and immunocompromised patients. The most common adverse events in previous clinical trials include injection-site pain (such as burning and itching) which was mild and lasted for less than 30 minutes, as well as fever, nausea, and flu-like symptoms which were mild to moderate in severity. Thus, while Ta1 is one of only a few immunomodulatory agents that have been approved for human use, it does not appear to induce most of the side effects and toxicities commonly associated with other biological response modifiers (BRMs) in this class, such as interferon and interleukin-2.

The actual dose, frequency, and length of treatment with Ta1 have differed depending upon the indication, ranging from 1.6 mg twice a week for up to 12 months; 1.6 mg twice a day for several weeks; 6.4 mg daily, 4 days a week, for 2 weeks out of every month up to 6 months in duration; and 16 mg twice a week for four weeks, with few adverse events observed. The proposal to evaluate Ta1 at a dose of 1.6 mg is based on previous studies which have shown an increase in dose above 1.6 mg to show little, if any, improvement in response.

Patients with end-stage renal disease (ESRD) on hemodialysis, in addition to their intrinsic kidney disease and frequent burden of comorbidities [20], also have increased risk of exposure to communicable diseases as they are treated several times each week at hemodialysis centers with several other patients and clinic staff in attendance. The majority of patients are over 60 years of age and many are receiving immunosuppressive medications. Accordingly, ESRD patients are particularly susceptible to COVID-19 infection. Ta1 has been shown to be safely administered to hemodialysis patients on a similar schedule to the one proposed below, and was efficacious in enhancing (> 4fold) the antibody responses to the influenza vaccine in geriatric & renal dialysis patients [1].

6 OBJECTIVES

6.1 Primary Objective

Primary Objective

To demonstrate that Ta1 administered twice weekly after dialysis for eight weeks to renal dialysis patients 60 years and older will reduce the incidence of COVID-19 infection over a six-month period compared with a similar population of patients who do not receive Ta1.

6.2 Secondary Objectives

Secondary Objectives:

1. To demonstrate that renal dialysis patients 60 years and older treated with Ta1 who become infected with COVID-19 will have a milder course of infection in terms of hospitalization rate, requirement for and length of ICU stay, requirement for mechanical ventilation, and survival than renal dialysis patients not treated with Ta1.
2. To demonstrate a decrease in hospitalization rates in renal dialysis patients treated with Ta1 who are not infected with COVID-19 compared to those not treated with Ta1.

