7 STUDY DESIGN

[figure not shown]
It is our hypothesis that a course of Ta1 administered to individuals at high risk for COVID-19 infection (hemodialysis patients 60 years and older) will reduce the rate of COVID-19 infection (primary objective) and severity of infection (secondary objective) with COVID-19, compared to untreated individuals in the same hemodialysis units with comparable risk. The secondary objectives also include an evaluation of the need for hospitalization in those patients who do not become infected with COVID-19.

Ideally, a randomized clinical trial with placebo control would be a preferred approach to address this hypothesis. However, the urgency of the current situation necessitates a simpler research design and implementation. Accordingly, we consider this a pilot study from which meaningful clinical data may rapidly be apparent.

After screening, renal dialysis patients 60 years and older who meet the inclusion criteria will receive Ta1 (1.6 mg) administered SC twice weekly for eight weeks. Individuals in the control arm will be followed on the identical protocol but will not receive twice weekly Ta1. After the treatment period, all subjects will be followed for efficacy outcomes for an additional 4 months. The total duration of the trial will be 1 year, including the estimated time required for screening.

A schema outlining the study design is presented in [Figure 1](#).

Figure 1: Study Design Schema

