8 ENDPOINTS

8.1 Primary Endpoint

The primary efficacy endpoint is reduction in documented infection with COVID-19. This is defined as clinical suspicion (presence of symptoms of respiratory infection; see Appendix 1 for questionnaire) and laboratory confirmation of COVID-19 infection.

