15.2 Data analysis plan

The primary goal of the analysis is to study the effect of the treatment on the outcome variables, in consideration of other covariates, including the demographic information and medical history of the participants and dialysis centers, which can potentially interact with the treatment. First, we will do an exploratory analysis of all the covariates altogether and stratified in the treatment and control group. We will study the effect of each of these covariates separately and together on the outcome. In the comprehensive study of all factors, we will build several models, including both parametric and tree-based models. We will also consider relevant interaction between the independent variables in the model. For the parametric models, we will use logistic regression for the binary outcomes, general linear regression (after a possible transformation of some covariates) for the continuous outcomes, Poisson regression with an over-dispersion test or a general log-linear model, for count outcomes, and a multinomial regression for the categorical variables with more than two categories. We will assess the fitted models based on model diagnostics and goodness-of-fit/prediction measures, such as adjusted R^2 , AIC, BIC, and cross-validation. A follow-up analysis will be done based on the results obtained from the various regression models. All the significant first-order and interaction effects will be further analyzed to understand the nature of the effect, and possibly considering further models stratified by relevant covariates.

Interim analyses will be done at least in the interval of 1, 3, and 6 months for the purpose of monitoring, presentations to the monitoring board, and any remedies (as needed) to ensure the quality of the study and safeguard the study population.

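### Both secondary objectives are framed by infection status, an outcome Ta1 is meant to change, and no all-randomised severity analysis is specified

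*Combined protocol and SAP*

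**What the plan says.** Secondary objective 1 (section 6.2) is that Ta1 patients "treated with Ta1 who become infected with COVID-19 will have a milder course of infection", judged on hospitalisation, ICU need and stay, ventilation and survival. Its comparator appears only at the end of the sentence: "requirement for mechanical ventilation, and survival than renal dialysis patients not treated with Ta1".

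Secondary objective 2 is "To demonstrate a decrease in hospitalization rates in renal dialysis patients treated with Ta1 who are not infected with COVID-19", again against those not given Ta1. The synopsis repeats both objectives, and section 7 describes the second as an "evaluation of the need for hospitalization in those patients who do not become infected with COVID-19".

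Section 6.1 states that Ta1 "will reduce the incidence of COVID-19 infection over a six-month period". Section 8.1 requires two things for an infection to count: "clinical suspicion (presence of symptoms of respiratory infection; see Appendix 1 for questionnaire) and laboratory confirmation of COVID-19 infection".

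Section 8.2 lists hospitalisation, ICU admission, ventilation, lengths of stay and mortality without restricting them to infected or uninfected patients, and section 11.1 collects them on every subject. Section 15.1 treats length of hospital stay as a continuous outcome, and section 15.2 assigns "general linear regression (after a possible transformation of some covariates) for the continuous outcomes". Section 15.2 gives model types and baseline covariates. It does not give an analysis population, an estimand for the severity outcomes, or a rule for patients who die.

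**The concern.** Randomisation balances the patients who were allocated. It does not balance groups defined by something that happens later and that treatment may influence. If Ta1 prevents infection more in one prognostic group than in another, infected Ta1 patients differ in prognosis from infected controls before severity is compared. The same applies to the uninfected groups.

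The section 8.1 definition adds to this. Symptoms are required as well as a positive test, although Table 1 schedules SARS-CoV2 assays whether or not symptoms are present. If Ta1 makes some infections symptom-free, those patients leave the infected group and join the uninfected one, so membership partly depends on severity.

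The duration outcomes have a related weakness. In a linear model of days in hospital or ICU, or on ventilation, a patient who dies early contributes a short value that looks favourable.

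The trial could therefore report worse or milder disease under Ta1 when severity given infection is unchanged, or fewer non-COVID hospitalisations when there is no such effect.

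**Working it through.** **1. The plan's own figure.** Section 15.1 assumes 0.40 infected on control, a detectable difference of 0.185 (so 0.215 on Ta1), 200 patients, a 0.05 level and 80% power. Allocation is 1:1, so 100 per arm. Sidedness is not stated; two-sided is used here.
- Log odds ratio (simple logistic regression): ln(0.215/0.785) − ln(0.40/0.60) = −0.890. SE = √[1/(100×0.40×0.60) + 1/(100×0.215×0.785)] = 0.318. Power = Φ(0.890/0.318 − 1.96) = 80.0%.
- Two-proportion test: 81.4%.

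The stated figure reproduces.

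**2. Subset sizes at those rates.** Infected: 100×0.40 = 40 controls and 100×0.215 = 21.5 on Ta1, 61.5 in all. Uninfected: 60 and 78.5.

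**3. Infected-only against all-randomised, no effect on severity.** The documents give no strata or hospitalisation rates, so these are assumptions: half the patients are robust and half frail; hospitalisation if infected is 20% and 60%; control infection is 40% in both strata; Ta1 infection averages 0.215.

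Let r and f be the Ta1 infection risks in robust and frail patients.
- All randomised, Ta1: 0.5×r×0.2 + 0.5×f×0.6
- Infected only, Ta1: that figure divided by 0.215
- Control: 0.5×0.4×0.2 + 0.5×0.4×0.6 = 0.160, and 0.160/0.40 = 40.0%

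| r / f | Infected only, control vs Ta1 | All randomised, control vs Ta1 |
|---|---|---|
| 0.215 / 0.215 (even) | 40.0% vs 40.0% | 16.0% vs 8.6% |
| 0.13 / 0.30 | 40.0% vs 47.9% | 16.0% vs 10.3% |
| 0.03 / 0.40 (strong) | 40.0% vs 57.2% | 16.0% vs 12.3% |
| 0.30 / 0.13 (frail benefit more) | 40.0% vs 32.1% | 16.0% vs 6.9% |

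Example, second row: 0.5×0.13×0.2 + 0.5×0.30×0.6 = 0.013 + 0.090 = 0.103, and 0.103/0.215 = 47.9%.

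**4. With a true severity benefit.** In the second row, suppose Ta1 lowers hospitalisation given infection by 10% in everyone. Infected only: 40.0% vs 0.9×47.9% = 43.1%, apparent harm. All randomised: 16.0% vs 0.9×10.3% = 9.3%, benefit. The infected-only sign is wrong for any true risk ratio between 40.0/47.9 = 0.83 and 1. In the strong row the lower limit is 40.0/57.2 = 0.70.

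**5. Uninfected only.** Assume background hospitalisation of 10% robust and 40% frail, unaffected by Ta1. Control: (0.30×0.10 + 0.30×0.40)/0.60 = 25.0%. Ta1, second row: (0.435×0.10 + 0.350×0.40)/0.785 = 23.4%. This is a small spurious benefit.

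**6. Comparator read literally as all controls.** Take even prevention, no effect on severity and the same background rates. All controls: 0.4×40% + 0.6×25% = 31%. Infected Ta1 patients: 40%, apparent harm. Uninfected Ta1 patients: 25%, apparent benefit. Both contrasts are artefacts, and here uneven prevention is not needed.

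**7. Precision.** With 40 vs 21.5 infected patients, a two-sided 5% test and control hospitalisation of 30 to 50%, the difference detectable with 80% power is 28 to 35 percentage points.

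**The case against.** The strongest reply is that only the objectives are conditional. The section 8.2 endpoints are unrestricted, the data are collected on everyone, and section 15.1 sizes continuous endpoints on about 200 patients, not on the infected. A reader might infer from section 6.2 that the whole plan analyses subsets only, or that it explicitly sets infected Ta1 patients against infected controls. The documents support neither: an all-randomised analysis is possible, and the control subset is never spelled out. What remains is that nothing requires that analysis, while the conditional questions are the ones the trial says it will demonstrate.

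Second, bias in a subset-against-subset comparison is not automatic. It needs uneven prevention, and no figure in the documents shows that. The strong row assumes almost complete prevention in robust patients and none in frail ones. Sections 15.1 and 15.2 also plan adjustment for age, Karnofsky score and comorbidity, which would remove part of the imbalance. This stands, but adjustment works only as far as those covariates capture what drives both infection and severity.

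Third, noise would often hide the bias. In the second row the SE is √(0.40×0.60/40 + 0.479×0.521/21.5) = 0.133, so the 0.079 shift is 0.6 SE. The chance of a nominally significant harm result is about Φ(0.6 − 1.96) = 9%; in the strong row it is about 26%. This limits the practical damage, but it also shows how little the infected-only comparison can establish.

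Fourth, this is a self-described pilot and these are secondary objectives. That lowers the priority, though it does not make the contrast valid.

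**Conclusion.** The point holds and should be fixed. Read as subset against subset, both secondary objectives lack the protection of randomisation. Read literally, against all controls, they are worse. Under uneven prevention the infected-only contrast can be biased either way and can reverse sign: 40% vs 48% among infected against 16.0% vs 10.3% in all randomised, with no effect on severity. These sizes rest on assumed strata and hospitalisation rates; only 0.40, 0.215 and 100 per arm come from the plan.

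A reader might infer that reversal is inevitable or that the trial's main result is compromised. Neither follows. If Ta1 prevents infection evenly, or not at all, the subset-against-subset comparison is not biased by this route. The primary infection comparison is made on the randomised arms and is unaffected.

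**What to change.** In the synopsis and sections 6.2, 8.2 and 15.2:

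- Base the comparative secondary analyses on all randomised patients by assigned arm: all-cause hospitalisation, ICU admission, ventilation and death.
- Add COVID-19 versions of these outcomes, with uninfected patients counted as no event. Define attribution by an objective rule, for example an event on or after a documented positive test, because section 8.2 separates COVID-19 from other causes only for mortality and the control arm has no placebo.
- State how the 40 expected dropouts of 240 are handled, by time-to-event censoring or a named missing-data method.
- Analyse length of stay and ventilation duration in all randomised patients by a rank-based method with death ranked worst, in place of a linear model.
- Keep infected-only and uninfected-only tables, labelled descriptive, and state their comparator.

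The underlying outcomes are already collected on everyone, so the cost is mainly wording plus agreement on the attribution and missing-data rules before results are seen. The real downside is that the all-randomised estimate combines the effect on infection with the effect on severity, so it does not isolate a milder course.
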